5.4 Statistical Analysis

5.4.1 Primary Efficacy Analysis

The analysis of the primary outcome will be performed on the EAS as the primary analysis and will be repeated on the PPS as a secondary analysis. Comparisons between the original treatment plan and the revised treatment plan will be categorised as no change, major change or other change. The definitions of the change categories are listed below.

- No change: the original treatment plan is the same as the revised treatment plan
- Major change: the original treatment plan is not the same as the revised treatment plan and the grouping for the original treatment plan is not the same as the grouping for the revised treatment plan

These will be further split and presented according to the following categories:

- Salvage or Non-curative systemic therapy to Watchful waiting
- Salvage therapy to Non-curative systemic therapy
- Non-curative systemic therapy to Salvage therapy
- Alternative Major change
- Other change: the original treatment plan is not the same as the revised treatment plan but the grouping for the original treatment plan is the same as the grouping for the revised treatment plan

These will be further split and presented according to the following categories:

- Modified RT field plan
- Modified androgen-deprivation regimen
- Alternative Other change

Groupings of treatment plans are detailed in the following table:

Date: 10OCT2018 Version: Amendment 1 Final

Version: Amendment 1 Fina ST/form/010/6

Original Treatment	Grouping for Original Tx Plan	Revised Treatment	Grouping for Revised Tx Plan
Was androgen deprivation therapy planned	Androgen Deprivation Therapy	Androgen deprivation therapy	Androgen deprivation therapy
		Watch and wait	Watch and wait
		Chemotherapy	Chemotherapy
Salvage radiotherapy to the prostate bed		Salvage radiotherapy to the prostate bed	
Salvage radiotherapy to the prostate bed, with boost to areas guided by conventional imaging	Salvage Radiotherapy	Salvage radiotherapy to the prostate bed, with boost to areas guided by conventional imaging	Salvage Radiotherapy
		Salvage radiotherapy to the prostate bed with boost to areas guided by fluciclovine (18F) PET/CT	
Salvage radiotherapy to the prostate bed and whole pelvis		Salvage radiotherapy to the prostate bed and whole pelvis	
Salvage radiotherapy to the prostate bed and whole pelvis, with boost to areas guided by conventional imaging	Salvage Radiotherapy	Salvage radiotherapy to the prostate bed and whole pelvis, with boost to areas guided by conventional imaging	Salvage Radiotherapy
		Salvage radiotherapy to the prostate bed and whole pelvis with boost to areas guided by fluciclovine (18F) PET/CT	

Date: 10OCT2018 Version: Amendment 1 Final ST/form/010/6

Original Treatment Plan	Grouping for Original Tx Plan	Revised Treatment Plan	Grouping for Revised Tx Plan
Salvage cryotherapy		Salvage cryotherapy	
	Salvage Cryotherapy	Salvage cryotherapy with boost to areas guided by fluciclovine (18F) PET/CT	Salvage Cryotherapy
Salvage brachytherapy		Salvage brachytherapy	
	Salvage Brachytherapy	Salvage brachytherapy with boost to areas guided by fluciclovine (18F) PET/CT	Salvage Brachytherapy
		Salvage brachytherapy with treatment plan guided by fluciclovine (18F) PET/CT	
Salvage HIFU		Salvage HIFU	
	Salvage HIFU	Salvage HIFU with treatment plan guided by fluciclovine (18F) PET/CT	Salvage HIFU
Salvage prostatectomy		Salvage prostatectomy	
	Salvage Prostatectomy	Salvage prostatectomy with targeted resection / sampling of fluciclovine (18F) positive areas outside conventional surgical field	Salvage Prostatectomy
Salvage prostatectomy and limited lymph node dissection		Salvage prostatectomy and limited lymph node dissection	

Date: 10OCT2018 Version: Amendment 1 Final ST/form/010/6

Original Treatment Plan	Grouping for Original Tx Plan	Revised Treatment Plan	Grouping for Revised Tx Plan
		Salvage prostatectomy and limited lymph node dissection with targeted resection / sampling of fluciclovine (18F) positive areas outside surgical field	
Salvage prostatectomy and extended lymph node dissection (including internal and external iliac, and obturator nodes)		Salvage prostatectomy and extended lymph node dissection (including internal and external iliac, and obturator nodes)	
		Salvage prostatectomy and extended lymph node dissection (including internal and external iliac, and obturator nodes) with targeted resection / sampling of fluciclovine (18F) positive areas outside surgical field	
		Targeted salvage treatment of fluciclovine (18F) positive extra-pelvic / bony areas	Targeted salvage treatment
		Other	Other

The classification and sub-classification of change in treatment management plan will be agreed prior to data base lock.

The number, percentage and exact 95% CI of subjects with and without a change in management plan after the fluciclovine (18F) scan results become available will be presented. In addition, the number and percentage of subjects with changes categorised as major or other will be presented. These summaries will be repeated separately for subjects with a positive and a negative fluciclovine (18F) scan and for subjects without prostatectomy and with prostatectomy.

Date: 10OCT2018 Version: Amendment 1 Final Page 17 of 22

The number, percentage and 95% CI of subjects who agreed to the revised management plan after fluciclovine (¹⁸F) scan results become available will be presented.

Details of the intended management plan, revised management plan and agreed management plan will be listed.

5.4.2 Secondary Efficacy Analyses

5.4.2.1 Treatment response as assessed by change in PSA

An assessment of treatment response, which is based on the percentage change in PSA from baseline to the last value reported, is defined as:

- >=30% decrease in PSA will be considered to be a response to treatment
- <25% increase or <30% decrease will be classified as stable disease
- >=25% increase in PSA will be classified as disease progression

See section 2 General Principles for baseline definition.

The number, percentage and exact 95% CI of subjects having a treatment response, stable disease and disease progression, as assessed by change in PSA, will be presented overall and separately for subjects in the FAS who had salvage treatment, for subjects who had non-salvage treatment, for those with a change in management plan and for subjects with no change in management plan following the ¹⁸F-fluciclovine PET/CT scan. In addition, treatment response assessed by change in PSA will be summarised by disease location (local disease versus extra-prostatic disease) and treatment administered.

The percentage change in PSA from baseline to the last value reported will be summarised overall and by subjects who had a change in management plan versus those who did not have a change in management plan following the ¹⁸F-fluciclovine PET/CT scan, disease location and treatment administered.

Finally, a waterfall plot of the maximum percentage reduction in PSA during the 4-8 month window will be presented on the y-axis and each subject will be represented by a bar on the x-axis. The bars will be ordered in descending order of the magnitude of the percentage change in PSA value.

Treatment response and the factors used to assess the response will be listed in full.

5.4.2.2 PSA threshold

The detection rate (DR) will be calculated as number of positive fluciclovine (¹⁸F) scan results/total number of scans.

Date: 10OCT2018 Version: Amendment 1 Final

The point estimate (expressed in percentage) of the DR will be presented at the region level and at the subject level. These rates will be presented for all subjects from the FAS and PPS, overall and across a range of baseline PSA values:

- 0 0.2
- \bullet >0.2 0.5
- \bullet >0.5 1.0
- \bullet >1.0 2.0
- \bullet >2.0 5.0
- \bullet >5.0 10.0
- >10.0

to determine the optimum PSA threshold for lesion detection. See section 2 General Principles for baseline definition.

The detection rates will also be summarised across the following baseline Gleason score categories: <=6, 7, 8 and >=9.

All fluciclovine (18F) and other imaging results will be listed.

Handling of Dropouts or Missing Data 5.4.3

Subjects who withdrew from the study prior to completion will be summarised. Withdrawn subjects will not be directly replaced and no imputation of missing data will be conducted.

5.4.4 **Interim Analyses and Data Monitoring**

A single interim analysis of the primary endpoint will be performed in the first 85 evaluable subjects. If the number of treatment changes is greater than 45 (52.9%, with a 97.5% two-sided CI of 40.3%-62.3%, so the lower limit is over 40%), the trial will be terminated early due to overwhelming effectiveness. If the number of treatment changes is 8 or fewer (9.4%, with a 97.5% two-sided CI of 3.6%-18.9%, so the upper limit in this population is below the 20% of the null hypothesis), the trial will be terminated early due to futility.

Examination of Subgroups

No subgroup analyses will be conducted during the study.

Site Specific Sub-study 5.4.6

A site specific sub-study will be conducted in order to compare the ordered subset expectation maximisation (OSEM) standard of care method of reconstructing PET/CT images with that of the Bayesian penalised likelihood method of PET/CT image reconstruction. The analysis of the sub-study results is beyond the scope of this SAP.

SAFETY EVALUATION

All safety evaluations will be performed on the safety analysis set (SAF) unless specified otherwise.

Date: 10OCT2018 Version: Amendment 1 Final

All safety tables will be presented by centre and overall.

Subjects will be included and counted in summary tables only if they have available data.

6.1 Adverse Events

Adverse events (AE) will be coded using the Medical Dictionary for Regulatory Activities (MedDRA) version 17.1.

A treatment-emergent adverse event (TEAE) is defined as an AE with start date/time on or after the start/time of fluciclovine (¹⁸F) administration, or AEs with worsening intensity on or after the start date/time of fluciclovine (¹⁸F) administration.

AEs with unknown start date/time will be assumed to be treatment-emergent unless the end date/time is known to be before the fluciclovine (¹⁸F) administration.

Summary tables will be produced for all TEAEs occurring up to 42 days (i.e. occurring between day 1 and day 43) after the fluciclovine (¹⁸F) administration.

An overall summary of TEAEs will be created including:

- number of TEAEs and number of subjects with TEAEs,
- number of TEAEs and number of subjects with TEAEs associated with the injection site,
- number of serious TEAEs and number of subjects with serious TEAEs,
- number of subjects with TEAEs by CTCAE grade (Grade 1 to Grade 5),
- number of subjects with TEAEs by relationship to fluciclovine (unrelated, possibly related, probably related, definitely related and related, where related adverse events are those classified as possibly, probably and definitely related to fluciclovine ¹⁸F)

The number and percentage of subjects experiencing TEAEs will be presented by system organ class (SOC) and preferred term (PT). System organ class and preferred term will be presented in decreasing frequency of the total number of subjects with TEAEs. If a subject experienced more than one treatment-emergent adverse event, the subject will be counted once for each system organ class and once for each preferred term.

The number and percentage of subjects experiencing TEAEs will be presented by SOC, PT and CTCAE grade. SOC and PT will be presented in decreasing frequency of the total number of subjects with TEAEs. If a subject experienced more than one TEAE, the subject will be counted once for each SOC and once for each PT at the worst severity.

The number and percentage of subjects experiencing TEAEs will be presented by SOC, PT and relationship to study drug. SOC and PT will be presented in decreasing frequency of the total number of subjects with TEAEs. If a subject experienced more than one TEAE, the subject will be counted once for each SOC and once for each PT at the closest relationship to study drug.

All adverse events will be listed and TEAEs will be identified. AEs occurring up to 42 days after fluciclovine (¹⁸F) administration will be flagged. All SAEs will be listed separately.

Date: 10OCT2018 Version: Amendment 1 Final

6.2 Clinical Laboratory Evaluation

6.2.1 Haematology

Haematology values will be summarised by parameter and visit, and also for change from baseline (last pre-scan value vs first post-scan value).

All haematology values will be listed showing reference ranges (flagging abnormal findings).

6.2.2 Biochemistry

Biochemistry values will be summarised by parameter and visit, and also for change from baseline (last pre-scan value vs first post-scan value).

Additionally, from the serum creatinine levels (mg/dL), creatinine clearance (CrCl) will be derived using the Cockcroft Gault formula (Cockroft DW, 1976) and the glomerular filtration rate (GFR) will be derived using the MDRD formula (Levey AS, 2006) as follows:

- Cockcroft-Gault formula: CrCl (mL/min) = [(140 age) * (Weight in kg) * (0.85 if female)] / (72 * Creatinine)
- MDRD formula: GFR (mL/min) = 175 * Creatinine^{-1.154} * age^{-0.203} * (1.212 if subject is black) * (0.742 if female)

CrCl and GFR categories (≤30 mL/min, >30 - ≤60, >60 - ≤90, >90 mL/min) will be summarised by time window, and the shift table of baseline status against the worst status on or after fluciclovine (¹8F) administration will be presented.

All biochemistry values will be listed showing reference ranges and flagging abnormal findings.

6.2.3 Urinalysis dipstick

All urinalysis results will be listed.

6.2.4 Urine microscopy

All urine microscopy results will be listed.

6.3 Vital Signs

Vital signs include pulse rate, systolic and diastolic blood pressure.

Vital sign values will be summarised by parameter and time point, and also for change from baseline.

Details of vital signs data will be listed.

6.4 Electrocardiography

Electrocardiogram (ECG) interpretation is recorded at screening and visit 4.

ECG interpretations will be summarised by shift tables highlighting any changes between screening and visit 4.

Date: 10OCT2018 Version: Amendment 1 Final

1 INTRODUCTION

This the second addendum to the final statistical analysis plan (SAP) Amendment 1 dated 10th October 2018, documenting additional analyses following database lock. Full details of the changes are detailed below.

2 CHANGES TO THE FINAL SAP

2.1 Change 1

Section 5.4.2.1 Treatment response as assessed by change in PSA

The number, percentage and exact 95% CI of subjects having a treatment response, stable disease and disease progression, as assessed by change in PSA, will be presented for subjects in the FAS who had salvage therapy. The summary will include an overall summary and separate summaries for subjects who had therapy guided by fluciclovine and for subjects whose therapy was not guided by fluciclovine.

This additional table will be of the same format as *Table 14.2.2.1 Treatment Response Assessment as Assessed by PSA - by Disease Location*, with the categories "Overall", "Local Disease" and "Extra-prostatic disease", replaced with "Salvage Therapy – All", "Salvage Therapy Guided by Fluciclovine" and "Salvage Therapy Not Guided by Fluciclovine" respectively.

This description is considered sufficient and a shell is not required. The title will be "Table 14.2.2.5 Treatment Response Assessment as Assessed by PSA in Subjects with Salvage Therapy - by Guided by/Not Guided by Fluciclovine".

Subjects will be determined to have a therapy guided by fluciclovine if they have an agreed therapy which contains the text string "GUIDED BY FLUCICLOVINE".

Reason for the change

To assess possible improvement in outcome of radical salvage treatment based on 18F fluciclovine PET/CT being included in the assessment.

2.2 Change 2

Section 5.4.2.3 Summary of disease location in subjects who had a change in management plan from salvage therapy to non-salvage therapy

The number and percentage of subjects who had positive extra-prostatic findings and negative extra-prostatic findings will be presented for subjects who had a change in management plan from salvage therapy to non-salvage therapy.

Subjects who had a change in management plan from salvage therapy to non-salvage therapy will be identified where the change of management plan is "SALVAGE THERAPY TO NON-CURATIVE SYSTEMIC THERAPY".

Positive/negative extra-prostatic findings will be determined from the imaging results.

This description is considered sufficient and a shell is not required. The title will be "Table 14.2.2.6 Presence of Extra-prostatic Disease in Subjects with Change of Management Plan from Salvage Therapy to Non-salvage Therapy".

Date: 08MAR2019 Version: Addendum 2 Final ST/form/038/1

Blue Earth Diagnostics study no: BED004

Syne qua non study no: BLS14004

Reason for the change

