First day of new management plan (Visit 6)

This will be performed as per standard of care and may be the same date as Visit 4, if the new management plan is commenced on the same day as the agreed treatment decision. During this visit, the investigator will record the date of management starting (to determine when follow-up information should be collected as detailed in the next heading “Clinical follow-up”).

Where patients are commencing radical salvage therapy, the investigator will also ensure that a pre-treatment PSA has been measured and recorded up to 31 days before this date.

All patients who receive radical salvage therapy

In this patient group, PSA will be measured a maximum of 31 days before therapy and at least once between 7-8 months after treatment completion. Where possible, this should be arranged to coincide with treatment-associated hospital visits as per standard of care. If these cannot be incorporated into the hospital visits, a minimum of one, maximum of two extra visits will be required for these PSA tests.

If the actual treatment received by the subject differs to the plan agreed at Visit 4, then this will be recorded on the “End of study” CRF (see the next section “Clinical follow-up”), along with the reason.

Clinical follow-up

Following instigation of their management plan, patients will be seen for follow-up at intervals as per standard of care and have imaging tests as clinically appropriate and per standard of care.

At the end of specified follow-up windows, follow-up information will be obtained by the local study team via attendance for imaging tests and via the GP or hospital medical care team as appropriate and entered on the “End of study” CRF. The patient will not be required to make a dedicated visit for this. The follow-up window is dependent on the type of management:

1. Radical salvage therapy: Up to the date of post-treatment PSA level check (7-8 months after completion of treatment).
2. Non-salvage management: Up to 6 months after Visit 6 (instigation of management plan).

In the event where radical salvage therapy is stopped prematurely or deemed by the clinical team to be sub-optimally delivered, the follow-up window should apply as for non-salvage management (up to 6 months from instigation of the initial management plan). The reasons for this should be recorded on the CRF as described in the prior section “All patients who receive radical salvage therapy”.

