5.4 Statistical Analysis

5.4.1 Primary Efficacy Analysis

The analysis of the primary outcome will be performed on the EAS as the primary analysis and will be repeated on the PPS as a secondary analysis. Comparisons between the original treatment plan and the revised treatment plan will be categorised as no change, major change or other change. The definitions of the change categories are listed below.

- No change: the original treatment plan is the same as the revised treatment plan
- Major change: the original treatment plan is not the same as the revised treatment plan and the grouping for the original treatment plan is not the same as the grouping for the revised treatment plan

These will be further split and presented according to the following categories:

- Salvage or Non-curative systemic therapy to Watchful waiting
- Salvage therapy to Non-curative systemic therapy
- Non-curative systemic therapy to Salvage therapy
- Alternative Major change
- Other change: the original treatment plan is not the same as the revised treatment plan but the grouping for the original treatment plan is the same as the grouping for the revised treatment plan

These will be further split and presented according to the following categories:

- Modified RT field plan
- Modified androgen-deprivation regimen
- Alternative Other change

Groupings of treatment plans are detailed in the following table:

Date: 10OCT2018 Version: Amendment 1 Final

Version: Amendment 1 Fina ST/form/010/6

Original Treatment Plan	Grouping for Original Tx Plan	Revised Treatment	Grouping for Revised Tx Plan
Was androgen deprivation therapy planned	Androgen Deprivation Therapy	Androgen deprivation therapy	Androgen deprivation therapy
		Watch and wait	Watch and wait
		Chemotherapy	Chemotherapy
Salvage radiotherapy to the prostate bed		Salvage radiotherapy to the prostate bed	
Salvage radiotherapy to the prostate bed, with boost to areas guided by conventional imaging	Salvage Radiotherapy	Salvage radiotherapy to the prostate bed, with boost to areas guided by conventional imaging	Salvage Radiotherapy
		Salvage radiotherapy to the prostate bed with boost to areas guided by fluciclovine (18F) PET/CT	
Salvage radiotherapy to the prostate bed and whole pelvis		Salvage radiotherapy to the prostate bed and whole pelvis	

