Salvage radiotherapy to the prostate bed and whole pelvis, with boost to areas guided by conventional imaging	Salvage Radiotherapy	Salvage radiotherapy to the prostate bed and whole pelvis, with boost to areas guided by conventional imaging	Salvage Radiotherapy
		Salvage radiotherapy to the prostate bed and whole pelvis with boost to areas guided by fluciclovine (18F) PET/CT	

Original Treatment Plan	Grouping for Original Tx Plan	Revised Treatment Plan	Grouping for Revised Tx Plan
Salvage cryotherapy		Salvage cryotherapy	
	Salvage Cryotherapy	Salvage cryotherapy with boost to areas guided by fluciclovine (18F) PET/CT	Salvage Cryotherapy
Salvage brachytherapy		Salvage brachytherapy	
	Salvage Brachytherapy	Salvage brachytherapy with boost to areas guided by fluciclovine (18F) PET/CT	Salvage Brachytherapy
		Salvage brachytherapy with treatment plan guided by fluciclovine (18F) PET/CT	
Salvage HIFU		Salvage HIFU	
	Salvage HIFU	Salvage HIFU with treatment plan guided by fluciclovine (18F) PET/CT	Salvage HIFU
Salvage prostatectomy		Salvage prostatectomy	
	Salvage Prostatectomy	Salvage prostatectomy with targeted resection / sampling of fluciclovine (18F) positive areas outside conventional surgical field	Salvage Prostatectomy
Salvage prostatectomy and limited lymph node dissection		Salvage prostatectomy and limited lymph node dissection	

Original Treatment Plan	Grouping for Original Tx Plan	Revised Treatment Plan	Grouping for Revised Tx Plan
		Salvage prostatectomy and limited lymph node dissection with targeted resection / sampling of fluciclovine (18F) positive areas outside surgical field	
Salvage prostatectomy and extended lymph node dissection (including internal and external iliac, and obturator nodes)		Salvage prostatectomy and extended lymph node dissection (including internal and external iliac, and obturator nodes)	
		Salvage prostatectomy and extended lymph node dissection (including internal and external iliac, and obturator nodes) with targeted resection / sampling of fluciclovine (18F) positive areas outside surgical field	
		Targeted salvage treatment of fluciclovine (18F) positive extra-pelvic / bony areas	Targeted salvage treatment
		Other	Other

The classification and sub-classification of change in treatment management plan will be agreed prior to data base lock.

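### Two selection rules in SAP Addendum 2 do not select the subjects their table labels describe

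*SAP*

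**What the plan says.** Addendum 2 documents analyses added after database lock.

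**Change 1 (section 2.1)** adds Table 14.2.2.5, PSA response in subjects who had salvage therapy, split into guided and not guided by fluciclovine. A subject is "guided by fluciclovine if they have an agreed therapy which contains the text string" `GUIDED BY FLUCICLOVINE`. The stated reason is the first secondary objective: possible improvement in the outcome of radical salvage treatment. The addendum says no table shell is needed.

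The plan options are printed in the grouping table of SAP 5.4.1. Some revised-plan options use the phrase, for example "Salvage HIFU with treatment plan guided by fluciclovine (18F) PET/CT". Others name fluciclovine without it, for example "Salvage prostatectomy with targeted resection / sampling of fluciclovine (18F) positive areas outside conventional surgical field" and "Targeted salvage treatment of fluciclovine (18F) positive extra-pelvic / bony areas".

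**Change 2 (section 2.2)** adds Table 14.2.2.6, presence of extra-prostatic disease in subjects moved from salvage to non-salvage therapy. The rule begins "Subjects who had a change in management plan from salvage therapy to non-salvage therapy will be identified where the change of management plan is" and then gives a single code, salvage therapy to non-curative systemic therapy. SAP 5.4.1 has three other major-change sub-categories. Two matter here: "Salvage or Non-curative systemic therapy to Watchful waiting" and "Alternative Major change".

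**The concern.** Each table would say something its selection rule does not support.

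In Table 14.2.2.5 the miss follows treatment type. A prostatectomy or extra-pelvic / bony plan cannot count as guided on its own wording, even when it names fluciclovine-positive areas as the target. Such a subject is reported as not guided unless another agreed item contains the string. The two rows would then partly separate treatment modalities, in a table meant to inform a secondary objective about outcome.

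In Table 14.2.2.6 a reader would take the percentage with extra-prostatic findings to cover everyone moved off salvage. It covers only those moved to systemic therapy.

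**Working it through.** The plan states no figure to reproduce. The check compares each rule with the option list and change categories in SAP 5.4.1.

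**Change 1: string against options.** The grouping table has 24 distinct revised-plan options. Twenty are salvage options and ten name fluciclovine; all ten are salvage. A case-insensitive search of those ten for `GUIDED BY FLUCICLOVINE` gives:

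| Type | Options naming fluciclovine | Matched |
|---|---|---|
| Radiotherapy | 2 | 2 |
| Cryotherapy | 1 | 1 |
| Brachytherapy | 2 | 2 |
| HIFU | 1 | 1 |
| Prostatectomy with targeted resection or sampling | 3 | 0 |
| Targeted extra-pelvic / bony | 1 | 0 |
| Total | 10 | 6 |

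So 10 − 6 = 4 options are missed. The search must ignore case, or the stored text must be upper case; a case-sensitive search of the text as printed matches 0 of 10.

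**Change 2: code against title.** SAP 5.4.1 has four major-change sub-categories, and the rule selects one.

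- The watchful-waiting category includes salvage as a starting plan by definition, and it is not selected.
- The residual category may also hold salvage to non-salvage moves. Its content is not defined, and it is not selected.
- Protocol 7.7 (Clinical follow-up) has two management classes, radical salvage therapy and "Non-salvage management: Up to 6 months after Visit 6 (instigation of management plan"). SAP 5.4.2.1 likewise contrasts salvage with non-salvage treatment. Watchful waiting therefore falls on the non-salvage side.
- The watchful-waiting category pools salvage and systemic starting plans. Adding that code alone would not repair the rule; the original plan is needed too.

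**Possible effect on the Table 14.2.2.6 percentage.** The documents give no counts, so these inputs are assumed. Suppose the table shows 18 of 20 positive (90%). Let *w* subjects be omitted, a proportion *q* of them positive. The full percentage is (18 + *qw*) / (20 + *w*):

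| *w* | *q* = 0 | *q* = 0.5 | *q* = 0.9 | *q* = 1 |
|---|---|---|---|---|
| 0 | 90.0% | 90.0% | 90.0% | 90.0% |
| 10 | 60.0% | 76.7% | 90.0% | 93.3% |
| 20 | 45.0% | 70.0% | 90.0% | 95.0% |

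When *w* is above zero, the direction depends only on whether *q* is below or above 0.9, which the documents do not give.

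**The case against.** **The string is applied to the agreed therapy, but option texts are printed only for the original and revised plans.** This stands as a limit. The four-of-ten count assumes that the agreed plan uses the revised-plan wording, so that must be confirmed first.

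**The rule was written after lock, so it may cover every option actually used.** This is possible. The number of subjects affected could be zero for either table, and the 45% to 95% range reflects chosen inputs rather than trial data. The addendum does not say that the unmatched options were unused.

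**The Table 14.2.2.6 title says non-salvage therapy, while the protocol's follow-up rule says non-salvage management; watchful waiting is arguably not a therapy.** This does not hold. The addendum's own heading and rule speak of a change in management plan, and watch and wait is one of the revised-plan groupings in SAP 5.4.1. The addendum does state its code openly, and the reason given for Change 2 is missing from the text available for this review. That gap is not counted against the plan.

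**The consequence is limited.** Both tables are descriptive. SAP 5.4.2.1 already summarises PSA response by treatment administered. The guided and not-guided groups are not randomised, so correcting the flag does not make their comparison causal. All of this stands; it bounds the importance of the point but does not make the labels accurate.

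**Reclassifying after lock is done with outcomes available, although SAP 5.4.1 says change classification is agreed before lock.** This is a fair caution. It applies to cases needing judgement, not to a fixed list of options.

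**Conclusion.** The point holds for both tables. On the printed option list, the Change 1 string misses 4 of the 10 salvage options naming fluciclovine: 0 of 3 prostatectomy and 0 of 1 extra-pelvic / bony options are matched, against 6 of 6 for the rest. These are options, not subjects. The count rests on the agreed-plan field sharing the revised-plan wording and on a search that ignores case.

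The Change 2 rule takes one of four major-change sub-categories and excludes salvage to watchful waiting by construction. The size and direction of its effect on the percentage are unknown.

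The reach is confined to two post-lock descriptive tables, one of which serves a secondary objective. The rules should be corrected because they can place subjects under a label that contradicts their recorded plan.

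**What to change.** **Change 1.** Confirm the wording stored in the agreed-plan field. Then define guided by an explicit list of all ten options naming fluciclovine, in place of the text string.

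**Change 2.** Either select subjects whose original grouping is salvage and whose revised grouping is non-salvage, with systemic therapy and watchful waiting in separate rows, or retitle the table so that it names non-curative systemic therapy as the destination.

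**Both.** State how many subjects each change reclassifies, including if that number is zero.

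The cost is small: some reprogramming and a revised addendum. Combined plans, and cases coded as other or as alternative major change, need adjudication. Because this would follow lock, it is best done without sight of PSA response or extra-prostatic findings. No new data are needed, since SAP 5.4.1 already lists the intended, revised and agreed plans.
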